5.7.6.7 Pain Freedom to 8 Hours Post-Dose

Pain freedom over time up to 8 hours will be analyzed using Kaplan-Meier methods. Kaplan-Meier estimates will be tabulated using the following time periods (0 through 30 minutes, > 30 through 60 minutes, > 60 through 90 minutes, > 90 through 120 minutes, >120 minutes through 180 minutes, >180 minutes though 240 minutes, >240 minutes though 360 minutes, >360 minutes though 495 minutes, and > 495 minutes). For each time period, the number of subjects at risk, with an event (pain freedom), censored, and survival probability estimate (with 95% CI), will be presented by treatment group. Subjects who fail to reach no pain by 495 minutes, will be censored at 495 minutes. Additionally, subjects who take rescue medication prior to 495 minutes will be censored at the date/time associated with their rescue medication. Note that the probability of survival corresponds to the probability of NOT having pain freedom. Survival estimates are calculated using the Kaplan-Meier product-limit method and median survival (time to pain freedom), and will be presented along with 95% CIs calculated using the method of Brookmeyer and Crowley.

To support the analysis, a Kaplan-Meier plot, with time in minutes on the x-axis and probability of survival on the y-axis, will be presented by treatment group. The number at risk at each time point (0, 15, 30, 45, 60, 90, 120, 180, 240, 360, and 495) minutes will be presented below the figure. In this analysis, being at risk corresponds to not yet having achieved pain freedom; therefore, the subject is still "at risk" of having pain freedom. Once a subject has pain freedom or is censored, then the subject is no longer in the risk pool. If a subject has missing data at an earlier time point, then the time point with missing data is not considered. The subject is still considered at risk of failure at a future time point if data are available. Subjects are censored as described above.

5.8 Pharmacokinetic Evaluations

No pharmacokinetic data were collected in this study.

6 SAFETY ANALYSIS

Safety analyses will be conducted on the treated population. All safety and other data will be listed. Subjects who were re-randomized will be considered as two individual subjects for the safety analyses. If such a subject is treated at least once with rimegepant, then their as-treated group assignment is rimegepant for all treatment occasions.

Safety outcome measures include: adverse events, laboratory assessments including liver toxicity, physical examinations, vital signs, physical measurements, ECGs, and concomitant medications.

Unless otherwise noted, baseline is considered as last assessment prior to study drug randomization.

6.1 Extent of Exposure

Extent of exposure is measured by subjects providing self-repored drug exposure information in their eDiaries. As a check on this exposure data, drug accountability data are provided by the study center on the "Drug Accountability" CRF page.

The self-reported exposure data will be tabulated by treatment group, and will include:

- The number (and percentage) of randomized subjects that took study medication
 - The number and percentage who took the medication prior to providing baseline study migraine migraine characteristics
 - The number and percentage that took study medication after providing baseline study migraine characteristics
- The number and percentage of randomized subjects who reported not taking study medication
- The number and percentage of randomized subjects for whom no expossure data was reported

The drug accountability will be tabulated by treatment and overall, and will include:

- The number and percentage of randomized subjects to whom kits were dispensed
- The number and percentage of kits returned
 - The number and percentage of kits returned from which the IP was used
 - The number and percentage of kits returned from which the IP was not used
- The number and percentage of kits not returned

A cross tabulation of exposure and accountability data will be prepared. This will be done overall. For the exposure data the categories are: Took IP, Did not Take IP, and Unknown. For the accountability data, the categories will be: IP Used, IP not Used, and Unknown.

A listing will be prepared that indicates the exposure and accountability status of all randomized subjects. A patient identifier (PID) lisiting will be prepared if subjects had unknown exposure data, unknown accountability data, or for whom the exposure and accountability data did not match.

6.2 Adverse Events

Adverse events (AEs) will be coded using MedDRA and displayed in tables and listings by system organ class (SOC) and preferred term (PT).

Analyses of AEs will be performed for those events that are considered on-study AEs with a start date prior to 30 days after the last dose of study medication. On-study is defined as any AE that developed, worsened, or became serious after study randomization.

Adverse events are summarized by subject incidence rates; therefore, in any tabulation, a subject contributes only once to the count for a given AE (SOC or PT).

The number and percentage of subjects with any on-study AE, with any on-study AE related to treatment (definite, probable, or possible relationship), with any on-study SAE, with any on-study severe AE, and with any on-study AE leading to discontinuation will be summarized by treatment group and overall. In these tabulations, each subject will contribute only once (i.e., the most related occurrence or the most intense occurrence) to each of the incidence rates in the descriptive analysis, regardless of the number of episodes.

No formal hypothesis-testing of AE incidence rates will be performed.

All AEs occurring pre-randomization and on-study will be listed. Additional listings will be provided including: deaths; SAEs; and AEs leading to discontinuation.

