4.2 Study Schematic

4.3 Schedule of Assessments

Table 1: Schedule of Assessments

Procedure	Screening Visit (3-28 days)¹	Baseline Visit (Randomization)¹	Onset of moderate or severe migraine²	During Treatment 15, 30, 45, 60 and 90 minutes Post-Dose	During Treatment 2, 3, 4, 6, 8 hours Post- Dose	During Treatment 24 hours Post-Dose	During Treatment 48 hours Post- Dose	End of Treatment Visit
Eligibility Assessments								
Informed Consent	X							
Inclusion/Exclusion Criteria	X	X						
Medical History	X							
Prophylactic Migraine Medication/ Concomitant Medication ³	X	X						X
Assessment of Migraine History (Signs and symptoms) paper source ¹⁴	X							
Safety Assessments								
Physical Examination	X							X
Vital Signs/Physical Measurements ⁴	X	X						X
Clinical Safety Laboratory Testing ⁵	X							X

Procedure	Screening Visit (3-28 days)¹	Baseline Visit (Randomization)¹	Onset of moderate or severe migraine²	During Treatment 15, 30, 45, 60 and 90 minutes Post-Dose	During Treatment 2, 3, 4, 6, 8 hours Post-Dose	During Treatment 24 hours Post-Dose	During Treatment 48 hours Post-Dose	End of Treatment Visit
ECG	X							X
Pregnancy Test ⁶	X	X	X					X
Adverse Event and Serious Adverse Event Assessment ⁷	X	X	X	X	X	X	X	X
Sheehan Suicidality Tracking Scale ⁸	X	X						X
Clinical Drug Supplies/Study Supplies								
Randomize ⁹		X						
Dispense Study Medication		X						
Administer 1 dose of study medication ¹⁰			X					
Return unused study medication								X
eDiary returned/reviewed for completeness ¹¹								X
Efficacy Assessments¹²								
Assessment of migraine pain ¹³			X	X	X	X	X	

Procedure	Screening Visit (3-28 days)¹	Baseline Visit (Randomization)¹	Onset of moderate or severe migraine²	During Treatment 15, 30, 45, 60 and 90 minutes Post-Dose	During Treatment 2, 3, 4, 6, 8 hours Post-Dose	During Treatment 24 hours Post-Dose	During Treatment 48 hours Post-Dose	End of Treatment Visit
Assessment of Migraine Symptoms (photophobia, phonophobia, and nausea - eDiary) ¹³			X	X	X	X	X	
Functional Disability Scale ¹³			X	X	X	X	X	
MQoLQ (Migraine Specified Quality of Life Questionnaire) ¹³						X		
Preference of Medication ¹³						X		

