4.3.2 Acute (Randomization) Phase (45 days)

If the patient meets all eligibility criteria they will be randomized at the Baseline Visit via the IWRS system. The patients will be provided with an eDiary. The study personnel will instruct the patient on the proper use of the eDiary and ensure proper understanding and use of the tool, prior to the patient leaving the office.

After randomization via the IWRS system, the patient will be dispensed a single dose of the double-blind study medication to take home for up to 45 days. This study medication is to be taken when a migraine attack reaches moderate or severe intensity on the numeric rating scale (NRS) as indicated in the eDiary. The patient will be instructed to take their study medication, as an outpatient, when (if) they have a migraine headache which reaches moderate or severe intensity **after they answer eDiary questions about their current pain and symptoms and identify their currently most bothersome, migraine associated, symptom (phonophobia, photophobia or nausea)**. The patient will complete an eDiary for up to forty-eight hours after taking study medication. The patient will telephone the study center immediately if a severe or serious adverse event occurs.

Patients will record efficacy data in their eDiary. This includes the following: onset time of headache, intensity of the headache prior to **and** at time of taking study medication. The patient should record all headache intensity leading up to dosing, but should not dose with study medication until the headache reaches moderate or severe intensity. Headache severity will be recorded using a four-point numeric rating scale (no pain, mild pain, moderate pain, severe pain) at the onset of the migraine and after dosing at time points of 15, 30, 45, 60, and 90 minutes and 2, 3, 4, 6, 8, 24 and 48 hours. The presence or absence of associated symptoms (nausea, photophobia, phonophobia) and ratings of functional disability (four-point scale: normal, mildly impaired, severely impaired, requires bedrest) will be recorded at the same time points as the headache severity ratings. Patients will also identify their currently most bothersome symptom before taking study medication. Patients will record the date and time study therapy was taken in their eDiary. Patients will also complete the migraine-specific quality-of-life questionnaire (MQoLQ) and preference of medication (PoM) 24 hours after

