8.2.1 Collection and Reporting of Non-Serious Adverse Events

The collection of non-serious AE information should begin at the Baseline visit. Non-serious AE information should also be collected from any observational period intended to establish a baseline status for a patient.

Non-serious adverse events should be followed until conclusion or stabilization, or reported as SAEs if they become serious. Follow-up is also required for non-serious AEs that cause interruption or discontinuation of study drug or those that are present at the end of study treatment.

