9.4.3 Analysis of Safety

The investigators determine the intensity of AEs and the relationship of AEs to study therapy. The investigators' terms are coded and grouped by system organ class using the

latest version of the Medical Dictionary for Regulatory Activities (MedDRA) available. AEs are presented by system organ class and preferred term, ordered by the overall frequency of events. If a subject had an adverse event with different intensities over time, then only the greatest intensity is reported.

AEs are tabulated in all treated subjects. SAEs occurring in subjects enrolled but not treated are listed. Deaths are listed for enrolled subjects without regard to onset.

The frequencies of the following safety events are summarized by treatment regimen, and overall, for treated subjects: SAEs; all AEs, non-serious AEs, AEs by intensity; and AEs by relatedness..

Graphical and tabular displays of liver function test results are provided.

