6.3 Laboratory Data

Clinical laboratory evaluations include:

- Hematology: hemoglobin, hematocrit, red blood cell count, white blood cell count with differential, and platelets
- Serum Chemistry: sodium, potassium, chloride, bicarbonate, calcium, glucose, BUN (urea), serum creatinine, uric acid, ALT, AST, alkaline phosphatase, LDH, total protein, albumin, total bilirubin, direct bilirubin, indirect bilirubin, CPK (with fractionation, if available)
- Lipid Panel: Cholesterol, LDL, HDL, triglycerides (screening only)
- Estimated glomerular filtration rate (eGFR) using the estimated MDRD formula will be calculated and reported by the central lab at each visit that the clinical laboratory test is collected.
- Urinalysis: pH, specific gravity, protein, ketones, nitrites, urobilinogen, leukocyte esterase, protein, glucose, microalbuminuria, and blood. If blood, protein, or leukocytes are positive, reflex to microscopic examination.
- Urine drug screen: for drugs of abuse

Clinical laboratory values will be expressed using both Standard US units and SI units. Tabulations, listings, and graphics will be provided to show the data in both systems. The observed value and change from baseline will be summarized for select continuous laboratory parameters. In addition, shift tables (low, normal, high) will be presented. For AST and ALT, the shift tables will use the categories: Normal, >ULN, >3x ULN, and >5x ULN. In the event of repeat values from the same visit, the non-missing value closest to the target date for the visit will be used. In the case of a tie, the latest record will be used.

All laboratory data will be provided in data listings. Additional listings will be presented for all abnormal laboratory values.

On-study laboratory abnormalities are those with an assessment date after the date/time of first dose of study drug and within 30 days after the last dose of study drug.

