14.2.3.8.10	Functional Disability Scale at Every Timepoint Post Dose:	mITT Subjects	
	Exploratory Analysis		
14.2.3.8.11	Sheehan-Suicidality Tracking Scale: Exploratory Analysis	mITT Subjects	
14.2.3.9.1	Kaplan-Meier Time to Pain Freedom: Exploratory Analysis	mITT Subjects	Y
14.2.3.9.2	Median Time to Pain Freedom	mITT Subjects	Y
14.3.1.1	Self-Reported Exposure Data Summary	All Randomized Subjects	
14.3.1.2	Drug Accountability Data Summary	All Randomized Subjects	
14.3.1.3	Cross Tabulation of Exposure and Accountability Data	All Randomized Subjects	
14.3.2.1	Summary of On-Study Adverse Events	Treated Subjects	Y
14.3.2.2	Incidence of On-study Adverse Events by System Organ Class and	Treated Subjects	Y
	Preferred Term		
14.3.2.3	Incidence of On-study Adverse Events Related to Study Drug by	Treated Subjects	
	System Organ Class and Preferred Term		
14.3.2.4	Incidence of On-study Serious Adverse Events by System Organ	Treated Subjects	Y
	Class and Preferred Term		
14.3.2.5	Incidence of On-study Adverse Events with Severe Grade by System	Treated Subjects	
	Organ Class and Preferred Term		
14.4.1.1	Hematology (SI Units): Observed and Change From Baseline Values	Treated Subjects	
	by Visit		
14.4.1.2	Hematology (UI Units): Observed and Change From Baseline	Treated Subjects	
	Values by Visit		
14.4.2.1	Serum Chemistry (SI Units): Observed and Change From Baseline	Treated Subjects	
1 4 4 9 9	Values by Visit	T 1011	
14.4.2.2	Serum Chemistry (US Units): Observed and Change From Baseline	Treated Subjects	
14421	Values by Visit	T 10.11	
14.4.3.1	Hematology (SI Units): Shift from Baseline by Visit	Treated Subjects	Y
14.4.3.2	Hematology (US Units): Shift from Baseline by Visit	Treated Subjects	Y
14.4.4.1	Serum Chemistry (SI Units): Shift from Baseline by Visit	Treated Subjects	Y
14.4.4.2.	Serum Chemistry (US Units): Shift from Baseline by Visit	Treated Subjects	Y
14.4.5.1	Urinalysis (SI Units): Shift from Baseline by Visit	Treated Subjects	
14.4.5.2	Urinalysis (SI Units): Shift from Baseline by Visit	Treated Subjects	

Table Number	Title	Population	Topline
14.4.6.1	Transaminases (SI Units): Shift from Baseline by Visit	Treated Subjects	Y
14.4.6.2	Transaminases (SI Units): Shift from Baseline by Visit	Treated Subjects	Y
14.4.7	Summary of On-Study Liver Toxicity	Treated Subjects	Y
14.5.1	Vital Signs and Physical Measurements: Observed and Change from Baseline Values by Visit	Treated Subjects	

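### On-study AEs are counted from randomization, up to 45 days before the single dose, and no planned table gives the post-dose AE rate

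*SAP*

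**What the plan says.** **AE clock.** SAP 6.2: "On-study is defined as any AE that developed, worsened, or became serious after study randomization". Only the upper limit, a start date earlier than 30 days after the last dose, refers to the dose. The partial-date rules in SAP 5.2.8 also compare with randomization.

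**Gap before the dose.** Protocol 4.3.2: "the patient will be dispensed a single dose of the double-blind study medication to take home for up to 45 days".

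**Collection before the dose.** Protocol 8.2.1: "The collection of non-serious AE information should begin at the Baseline visit". SAEs are collected from consent.

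**Presentation.** Protocol 9.4.3: "The frequencies of the following safety events are summarized by treatment regimen, and overall, for treated subjects: SAEs; all AEs". SAP Appendix 1 lists Tables 14.3.2.1 ("Summary of On-Study Adverse Events") to 14.3.2.5, and Appendix 4 adds 14.3.2.6. All six are on-study tables, and the AE listings are split at randomization.

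**Laboratory clock.** SAP 6.3: "On-study laboratory abnormalities are those with an assessment date after the date/time of first dose of study drug".

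**The concern.** Being dosed decides which subjects are counted in the AE tables, but not which of their events are counted. A subject who caught a cold two weeks after randomization and took the tablet a week later contributes that cold to the any-AE and SOC/PT rates of the assigned arm. A pre-dose SAE or severe AE is treated the same way.

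Such events say nothing about the tolerability of one 75 mg tablet. Blinded randomization should balance them, so the expected effect is dilution: inflated absolute rates in both arms and a relative risk closer to 1. These are the trial's headline tolerability rates for a single dose, and a reader could not recover the post-dose rate from any planned table.

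A secondary point, of wording only, concerns re-randomized subjects. SAP Section 6 counts each as two individuals. SAP 5.2.7 is worded for one subject with one actual treatment and an AE window that opens at the first randomization. Counting unit and window need to agree.

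**Working it through.** **Is the 45-day window consistent with the plan's own figure?** Maximum phase lengths in Protocol 4.1 are 28 + 45 + 7 = 80 days, and 80/7 = 11.4 weeks. The protocol states approximately 11 weeks, so the window is confirmed.

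**Longest possible wait.** The pre-dose segment is 45/(45+7) = 87% of the time from randomization to the 7-day End of Treatment target, or 45/(45+30) = 60% of the time to the 30-day limit in SAP 6.2.

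**Typical wait (assumption).** Take exponential waits at the eligible attack rates in Protocol 5.2, λ = 2/30 and 8/30 per day, among subjects who dose within 45 days:

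w = 1/λ − 45·exp(−45λ)/(1 − exp(−45λ))

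This gives w = 12.64 days at 2 attacks per month and 3.75 days at 8.

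**Pre-dose share of background AEs.** Let f be the days of post-dose capture and k the ratio of the pre-dose to the post-dose recording rate:

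s = k·w/(k·w + f)

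The documents do not give k. The schedule row "Adverse Event and Serious Adverse Event Assessment" has no entry between Baseline and migraine onset, so k below 1 is plausible.

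| k | f = 7: 8 / 2 attacks per month | f = 30: 8 / 2 attacks per month |
|---|---|---|
| 1 | 0.349 / 0.644 | 0.111 / 0.296 |
| 0.5 | 0.211 / 0.475 | 0.059 / 0.174 |
| 0.25 | 0.118 / 0.311 | 0.030 / 0.095 |

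**Effect on the relative risk.** For rare events the background rate cancels:

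RR(on-study) = 1 + (1 − s)·(RR(post-dose) − 1)

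An assumed post-dose RR of 2 would show as 1.36–1.89 (k = 1), 1.53–1.94 (k = 0.5) or 1.69–1.97 (k = 0.25).

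**Check of the approximation.** Exact risks were averaged over the truncated wait, with an assumed drug-attributable risk of 5%, background 0.25% or 1% per day, f = 7 or 30, k = 1 or 0.5, and both attack rates (16 cases). The approximation is within 0.01 of the exact RR throughout, for example 2.009 against 2.001 and 1.246 against 1.238.

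**Effect on the risk difference and absolute rate.** If b is the risk of a pre-dose AE, RD(on-study) = (1 − b)·RD(post-dose). The largest fall in the 16 cases is from 4.66 to 4.13 points (1% per day, f = 7, 2 attacks per month, k = 1). In that case the placebo AE rate shows as 17.4%, while the post-dose rate is 1 − exp(−0.07) = 6.8%.

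**A second illustration, with fixed risks.** Assume post-dose AE risks of 15% and 10% (RR 1.50, RD 5.0 points).

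| Pre-dose AE risk, both arms | On-study RR | On-study RD (points) |
|---|---|---|
| 2% | 1.42 | 4.9 |
| 5% | 1.33 | 4.75 |
| 10% | 1.24 | 4.5 |
| 15% | 1.18 | 4.25 |

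**The case against.** The strongest reply is that this is an explicit, prespecified definition whose effect favours neither arm. SAP 6.2 plans no hypothesis tests on AE rates, safety sits among the exploratory objectives, and the planned summaries are counts and percentages, not relative risks. On the difference scale the change is under one point in every case worked. All of that stands, and it limits the weight of the point.

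The upper end of the range is also extreme. A share of 64% needs every subject at the minimum attack rate, capture that stops at 7 days, and equal recording before and after dosing. That stands too, and it is why lower recording rates are shown.

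The laboratory contrast is mostly drafting. Scheduled safety laboratory tests after randomization occur only at End of Treatment, so either anchor selects nearly the same results. The liver table in SAP 6.3.1 itself counts measurements from randomization. In that table only the row that pairs a transaminase elevation with a symptom AE is affected.

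Table 14.3.2.3 (related AEs) should screen out most pre-dose events. It does so through investigator causality, not timing, and it leaves the any-AE, SAE, severe-AE and SOC/PT tables as they are.

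Finally, randomization is a firmer anchor than a self-reported dose. SAP 6.1 allows for missing exposure data: "For the exposure data the categories are: Took IP, Did not Take IP, and Unknown". That calls for a rule for unknown dose times and is no reason to leave the post-dose rate unreported. Protocol 9.4.3 sets no dose anchor, so the SAP does not contradict it. The proposal adds to what the protocol requires.

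**Conclusion.** The concern holds. In treated subjects the AE tables mix unexposed and exposed time, and none of the six is anchored to the dose. The consequence is dilution without expected directional bias: higher AE rates in both arms, a relative risk nearer 1, and a slightly smaller risk difference.

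The direction does not depend on the assumptions. The size does, because background AE rates, pre-dose recording and actual waits are not in the documents. Efficacy conclusions, alpha and sample size are untouched. This should be corrected because the main tolerability rates would otherwise not describe what follows the tablet. The re-randomization wording is a minor addition, and the number of such subjects is not given.

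**What to change.** - Add treatment-emergent AE tables by treatment group and make them the main tolerability tables. Count an AE that starts, worsens or becomes serious at or after the dose date and time and within the existing 30-day limit.
- Count as post-dose any same-day event with no onset time, and any event in a treated subject with no recorded dose time.
- Use the same anchor for the symptom row of the liver table in SAP 6.3.1 and, for these tables, in the partial-date rules of SAP 5.2.8.
- Keep the on-study AE and SAE summaries that Protocol 9.4.3 calls for, and show events between randomization and dose separately by arm.
- Reconcile the counting unit and AE window for re-randomized subjects between SAP 5.2.7 and Section 6, and report how many there were.

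The cost is SAP wording and one more set of tables. No new data are needed, because Protocol 4.3.2 already has subjects record the dose date and time in the eDiary. There are two drawbacks: two AE displays must be clearly labelled, and the rule for unknown times will count some pre-dose events as post-dose.

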2.3 Exploratory

- To evaluate the effect of rimegepant (75 mg tablet) relative to placebo on the patients ability to work or function at 24 hrs post dose according to the Functional Disability scale.
 - To evaluate rimegepant (75 mg tablet) compared to placebo on **pain relief at 90** minutes post-dose.
 - To evaluate rimegepant (75 mg tablet) compared to placebo on **pain relief at 60** minutes post-dose.
 - To evaluate rimegepant (75 mg tablet) compared to placebo on **pain relief at 30** minutes post-dose.
 - To evaluate the effect of rimegepant (75 mg tablet) relative to placebo on the **Migraine Preference of Medication (PoM)**
 - To evaluate rimegepant (75 mg tablet) relative to placebo for pain relief on the 4 point scale at all scheduled time points post dose
 - To evaluate the effect of rimegepant (75 mg tablet) relative to placebo on the **Migraine Quality of Life (MQoLQ)**
 - To evaluate the **tolerability and safety** of rimegepant (75 mg tablet) in the acute treatment of migraine as measured by the frequency of adverse events of at least moderate intensity, serious adverse events; and clinically relevant laboratory abnormalities.
 - To evaluate the effect of rimegepant (75 mg tablet) relative to placebo on the **Sheehan Suicidality Tracking Scale**.
-

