1.2.3 Exploratory Objectives

- To evaluate the effect of rimegepant (75 mg tablet) relative to placebo on the subjects' ability to work or function at 24 hours post-dose according to the Functional Disability Scale.
- To evaluate the effect of rimegepant (75 mg tablet) relative to placebo on pain relief at 90 minutes post-dose.
- To evaluate the effect of rimegepant (75 mg tablet) relative to placebo on pain relief at 60 minutes post-dose.
- To evaluate the effect of rimegepant (75 mg tablet) relative to placebo on pain relief at 30 minutes post-dose.
- To evaluate the effect of rimegepant (75 mg tablet) relative to placebo on the Migraine Preference of Medication (PoM) at 24 hours post-dose.
- To evaluate the effect of rimegepant (75 mg tablet) relative to placebo on pain relief on the 4-point scale at all scheduled time points post-dose.
- To evaluate the effect of rimegepant (75 mg tablet) relative to placebo on the Migraine Quality of Life Questionnaire (MQoLQ) at 24 hours post-dose.
- To evaluate the tolerability and safety of rimegepant (75 mg tablet) in the acute treatment of migraine as measured by the frequency of adverse events of at least moderate intensity, serious adverse events, and clinically relevant laboratory abnormalities.
- To evaluate the effect of rimegepant (75 mg tablet) relative to placebo on the Sheehan Suicidality Tracking Scale (S-STS) at end of treatment.

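### The SAP drops the protocol's summary of adverse events by intensity without declaring it, so one of three measures of the exploratory safety objective has no specified table

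*SAP*

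**What the plan says.** The objective is worded almost identically in the two documents. SAP 1.2.3 measures tolerability and safety by the "frequency of adverse events of at least moderate intensity, serious adverse events, and clinically relevant laboratory abnormalities"; Protocol 2.3 names the same three measures.

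Protocol 9.4.3 lists the safety summaries to be made by treatment regimen and overall in treated subjects. The list ends with "AEs by intensity; and AEs by relatedness". The same section says that investigators determine intensity, and that a subject whose event varied in intensity is reported at the greatest one.

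SAP 6.2 sets out the AE summary. It counts subjects with any on-study AE and with a treatment-related AE, and then "with any on-study SAE, with any on-study severe AE, and with any on-study AE leading to discontinuation". In SAP Appendix 1, Tables 14.3.2.1 to 14.3.2.5 cover the overall summary, all AEs, related AEs, serious AEs and severe AEs. The title of Table 14.3.2.5 begins "Incidence of On-study Adverse Events with Severe Grade by System". The one AE table added among the supportive analyses (14.3.2.6, Appendices 3 and 4) concerns events leading to discontinuation.

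SAP Section 7, on changes from the protocol, reports only additional supportive analyses.

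**The concern.** The objective sets its AE cut-off at moderate; the SAP sets its only intensity cut-off at severe. Moderate events enter the planned tables only inside the any-AE count, together with mild ones. A programmer who produces exactly what the SAP lists will have no table showing, by arm, how many subjects had an AE of at least moderate intensity. Apart from SAEs, that is the only AE measure the objective names.

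The omission is also silent. Someone comparing the two documents through SAP Section 7 would conclude that the protocol's safety summaries were all retained and some analyses added. At stake is traceability from a stated objective to a planned output, and a descriptive safety figure that readers of the study report would expect to find.

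**Working it through.** The plan states no figure to reproduce, so the check is a comparison of texts followed by a short counting argument.

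**Step 1: match each measure of the objective to a planned SAP output.**

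| Measure (Protocol 2.3, SAP 1.2.3) | Planned output in the SAP |
|---|---|
| AEs of at least moderate intensity | None specified |
| Serious AEs | Row of the AE summary (14.3.2.1); Table 14.3.2.4 |
| Clinically relevant laboratory abnormalities | Shift tables, liver toxicity table (14.4.7), eDISH plot, listings of abnormal values |

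The Safety and Tolerability row of SAP Table 3 does not fill the gap. It gives the variables only as multiple and refers to Section 6, which does not contain the measure.

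**Step 2: ask whether the missing frequency follows from the planned counts.** Classify each treated subject with an AE by maximum intensity, and let n1, n2 and n3 be the numbers whose maximum is mild, moderate and severe.

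- Any AE: A = n1 + n2 + n3 (planned).
- Severe AE: S = n3 (planned).
- At least moderate: M = n2 + n3 (the objective's measure).

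The planned counts give only n1 + n2 = A − S. They do not divide that sum between mild and moderate. If all of it is mild, M = S; if all of it is moderate, M = A. So S ≤ M ≤ A, and the undetermined range has width A − S in each arm. The other planned categories (related, serious, leading to discontinuation) classify events on different axes and do not fix n2. The documents as available give no AE rates for this trial, so the width cannot be put in numbers without inventing them.

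**Step 3: ask whether the protocol's summary would have supplied it.** A table by intensity with each subject counted at the greatest intensity, as in Protocol 9.4.3, gives n1, n2 and n3 directly, and M is the sum of the last two. The measure is lost at the step from protocol to SAP.

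**Step 4: check whether the change is declared.** SAP Section 7 and Appendix 3 mention no removal or replacement of the by-intensity summary.

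**The case against.** Several points can fairly be made for the plan.

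- **The protocol commitment still stands.** Nothing in the SAP withdraws the summary in Protocol 9.4.3, so it may yet be produced. This is correct, and it rules out the reading that the measure will never be reported. However, SAP 1.1 presents the SAP as the source of the planned summary tables for the study report, so a commitment without a table there is still a gap.
- **The SAP has a maximum-intensity rule.** In the Section 6.2 tabulations "each subject will contribute only once (i.e., the most related occurrence or the most intense occurrence", which is the kind of rule one needs when classifying by intensity. Appendix 1 gives titles without table shells, so a breakdown inside Table 14.3.2.1 or 14.3.2.2 cannot be excluded. But the rule is attached to five named categories, none of which is a moderate level, and no text or title specifies such a breakdown.
- **The data are not lost.** All AEs are listed and investigators grade intensity. A by-subject listing is not a frequency by treatment group, but it does mean that a table could be built at any time.
- **The objective is broader than this one measure.** A reader might infer that the trial fails to report its own tolerability objective, or that the SAP tabulates nothing but any and severe AEs. The documents support neither. SAEs and laboratory abnormalities have planned outputs, and related AEs and AEs leading to discontinuation are tabulated too. The contrast between any and severe holds only for intensity cut-offs.

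**Conclusion.** The point holds as a mismatch between protocol and SAP. The by-intensity AE summary of Protocol 9.4.3 is neither carried forward nor declared as dropped, and one of the three measures of an exploratory objective is left without a specified table. The planned any-AE and severe-AE counts bound that measure but do not determine it.

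The impact is minor. SAP 6.2 plans no hypothesis test on AE rates, and the co-primary analyses and type I error are untouched. Safety data collection and the serious, severe and liver outputs are also unaffected. The conclusion rests on the text of SAP 6.2 and on table titles, since no table shells are available. A shell that already splits Table 14.3.2.1 by intensity would reduce the point to stating that in the text.

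**What to change.** 1. Add a row to Table 14.3.2.1 for subjects with any on-study AE of moderate or severe intensity, and name it in SAP 6.2.
2. Make Table 14.3.2.5 a table by maximum intensity per subject (mild, moderate, severe), by treatment group and overall, in treated subjects. Its severe column keeps everything the present table would show.

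If the sponsor prefers not to present the measure, the alternative is to reword the objective and record in SAP Section 7 that the by-intensity summary has been dropped.

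The cost is one added row and one changed table, with no new data collection. Because the output is descriptive, it can be added without any multiplicity consequence.
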